### 3.3. CHANGES TO ANALYSIS FROM PROTOCOL

The visit window in the protocol is -5/+14 days for visits 2, 3 and 4. For the statistical analysis this window will be -7/+28 days for each visit.

There are no other changes to planned analyses in the protocol. However, during special circumstances such as the COVID-19 pandemic, the specific guidance from local public health and other competent authorities regarding the protection of individuals' welfare will be applied. For the duration of such special circumstances, some measures may impact the data and analysis:

- Delayed FPI
- Protocol deviations due to COVID-19
- Missed visits due to COVID-19
- Missed or modified assessments
- Treatment interruptions or delays
- Early study discontinuation or withdrawals due to having COVID-19 or COVID-19 related issues
- Adverse events or SAEs due to COVID-19

The number and percentage of participants experiencing any of the COVID related consequences listed above will be presented.

## 4. PLANNED ANALYSES

The following analyses will be performed for this study:

- Interim analysis
- Final Analysis

### 4.1. DATA MONITORING COMMITTEE (DMC)

There will be no DMC for this study.

---

Document: C:\ProgramData\activePDF\Temp\DocConverter\API\input\99638a57dafd\$76D9DDEF7D8D4E7C  
B4DEE6C228977964.docx

Author: PPD

Version Number:

Final 5.0

**CONFIDENTIAL**

Version Date:

05SEP2022

## 4.2. INTERIM ANALYSIS

An interim analysis of safety objectives will be conducted after at least 50% of participants have completed Visit 4. An interim analysis of immunological objectives may also be performed after all participants have completed Visit 4. If performed, the assessment of the primary immunological objectives will follow the order described in section 16.1.3 with analysis of family 1 preceding that of family 2.

The interim analysis will be performed by the unblinded analysis team who are independent of the blinded analysis team. Only unblinded analysis tables will be provided to avoid the reviewer being unblinded at a participant level.

## 4.3. FINAL ANALYSIS

All final, planned analyses identified in this SAP will be performed by IQVIA Biostatistics following GlaxoSmithKline authorization of this Statistical Analysis Plan, Database Lock, Sponsor Authorization of Analysis Sets and Unblinding of intervention.

## 5. ANALYSIS SETS

Agreement and authorization of participants included/excluded from each analysis set will be conducted prior to the unblinding of the study.

### 5.1. PROCESS FOR ANALYSIS SET ASSIGNMENT

- Preliminary analysis sets will be derived, prior to the database lock, to the extent that data is available.
- Data listings presenting participants excluded from each preliminary analysis set and reasons for exclusion will be prepared for sponsor review ahead of database lock (during the data review meeting) in order to allow appropriate related data queries to be issued.
- The final analysis sets will be derived after database lock and will use the final study data, i.e., clinical database (CRF), external vendor data (serological results), eDiaries and protocol

---

Document: C:\ProgramData\activePDF\Temp\DocConverter\API\input\99638a57dafd\$76D9DDEF7D8D4E7C  
B4DEE6C228977964.docx

Author: PPD

Version Number:

Final 5.0

**CONFIDENTIAL**

Version Date:

05SEP2022

- deviations log.
- Data listings presenting participants excluded from each final analysis set and reasons for exclusion will be prepared for sponsor review ahead of unblinding for a final review and approval.
  - Customer authorization of the analysis sets will be necessary to unblind the data after database lock.

## 5.2. ENROLLED SET [ENR]

The enrolled set (ENR) will contain all participants who agreed/participants for whom parent(s)/legally acceptable representative agreed to participate in a clinical study after completion of the informed consent process, who meet screening/eligibility criteria and randomized or received study intervention or undergone an invasive procedure.

For analyses and displays based on ENR, participants will be classified according to randomized intervention.

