9.3 Populations for Analyses

Populations for analyses in this study are defined in [Table 15](#).

Table 15 Populations for Analyses

Analysis set	Description
Enrolled Set (Enr)	Participant who agreed/participant for whom parent(s)/LAR(s) agreed to participate in a clinical study after completion of the informed consent process and randomized or received study intervention or undergone an invasive procedure.
Exposed Set (ES)	All participants who received at least 1 dose of the study intervention. The allocation in a group is done in function of all administered interventions.
Full Analysis Set (FAS)	All participant who received at least 1 dose of the study intervention and have post-vaccination immunogenicity data
Per Protocol Set (PPS)	All participants who received at least 1 dose of the study intervention to which they are randomized and have post-vaccination data (FAS) minus participants with protocol deviations that lead to exclusion from the PPS.
Unsolicited Safety Set (USS)	All participants who received at least 1 dose of the study intervention (ES) that report unsolicited AEs/report not having unsolicited AEs
Solicited Safety Set (SSS)	All participants who received at least 1 dose of the study intervention (ES) that report solicited safety data

AE = adverse event; LAR = legally acceptable representative

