## 9.2. PROTOCOL DEVIATIONS

Protocol deviations will be collected in a PD log, as detailed in the Protocol Deviations Management Plan.

All protocol deviations will be assessed as important or non-important. Protocol deviations will be reviewed by the GSK Team, and their status confirmed by the time that all data are cleaned for the Final Analysis. APPENDIX 3 lists PDs that affect the validity of the immunogenicity measurements and result in exclusion of participants from the PPS.

A summary presenting the number and percentage of participants in each PD category will be presented for participants in the ENR set, by vaccine group and overall, and a data listing will be provided for participants with protocol deviations during the study. Additionally, a data listing of PDs for participants who are excluded from the PPS will be generated.

A summary presenting the number and percentage of participants with a protocol deviation related to COVID-19 in each PD category will be presented for participants in the ENR set, by vaccine group and overall. Additionally, PDs related to COVID-19 will be flagged in the PD listing.

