**Exclusion from Full Analysis Set (FAS)**

‘Study intervention not administered at all’, missing laboratory (Immunology) assessment (missed visit, blood draw not done at visit, sample not available for testing, result not available) and ‘Fraudulent data’ will be used for identifying participants excluded from the FAS.

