**Table 3: Protocol deviations mapping and exclusion from analysis sets**

CTMS * Categories	GSK Deviations Code/ Description	Visit (timepoints) where the exclusion is applicable
1. Informed Consent Criteria	1A - Signed informed consent/assent not available on site	All
	1B - Wrong informed consent/assent version signed	All
	1C - Informed consent/assent not signed and/or dated by participant (parent/Legal rep)	All

Document: C:\ProgramData\activePDF\Temp\DocConverter\API\Input\99638a57dafd\$76D9DDEF7D8D4E7C  
 B4DEE6C228977964.docx

Author: PPD

Version Number: Final 5.0

**CONFIDENTIAL** Version Date: 05SEP2022

CTMS * Categories	GSK Deviations Code/ Description	Visit (timepoints) where the exclusion is applicable
	1D – Informed consent/assent not signed and/or dated by appropriate site staff	
	1E - Informed consent/assent not signed prior to any study procedure	All
	1OT - Other informed consent/assent deviations	All Manual case-by-case review
	3A - Not withdrawn from study after developing withdrawal criteria	All Manual case-by-case review
2. Eligibility and Entry Criteria	2 - Eligibility criteria not met	All
	7A - Study treatment not administered per protocol	By visit for Day 31 and Day 211 (based on treatment administered on Day 1 and Day 181 respectively)
	7B - Study treatment administered while contraindication	By visit for Day 31 and Day 211 (based on treatment administered on Day 1 and Day 181 respectively) Manual case-by-case review
	8A - Randomization procedure (subj assigned to wrong treatment, subj rand out of order)	All

Document: C:\ProgramData\activePDF\Temp\DocConverter\API\Input\99638a57dafd\$76D9DDEF7D8D4E7C  
 B4DEE6C228977964.docx

Author: PPD

Version Number: Final 5.0

**CONFIDENTIAL** Version Date: 05SEP2022

CTMS * Categories	GSK Deviations Code/ Description	Visit (timepoints) where the exclusion is applicable
3. Concomitant Medication Criteria	4A - Medication, excluded by the protocol, was administered	By visit for Day 31 and Day 211 (based on treatment administered on Day 1 and Day 181 respectively)
	4B - Vaccine, excluded by the protocol, was administered	By visit for Day 31 and Day 211** (based on treatment administered on Day 1 and Day 181 respectively).
4. Laboratory Assessment Criteria	8G - Biological sample specimen procedures	By visit for Day 31 and Day 211 (based on treatment administered on Day 1 and Day 181 respectively)

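### The SAP's Enrolled Set adds an undeclared eligibility condition, and its Full Analysis Set exclusion list omits invalid consent

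*SAP*

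**What the plan says.** **Enrolled Set.** Protocol 9.3, Table 15, takes participants "after completion of the informed consent process and randomized or received study intervention or undergone an invasive procedure". SAP 5.2 takes those "who meet screening/eligibility criteria and randomized or received study intervention or undergone an invasive procedure". SAP 3.3 declares a wider visit window for analysis and then states: "There are no other changes to planned analyses in the protocol".

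**Where ENR is used.** SAP 9.1 reports disposition by group for ENR, including reasons for exclusion from analysis sets. SAP 9.2 says: "A summary presenting the number and percentage of participants in each PD category will be presented for participants in the ENR set". For individual participants, the same section adds that "a data listing will be provided for participants with protocol deviations during the study", with a further listing of deviations for those left out of the PPS. SAP 5.1 plans listings of exclusions from each analysis set, with reasons. One deviation code in Appendix 3, Table 3, is "2 - Eligibility criteria not met"; it removes the participant from the PPS at all visits.

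**Consent.** Appendix 3 names invalid informed consent among the exclusions from the ES, the unsolicited safety set and the solicited safety set. Table 3 applies consent deviations to the PPS, generally at all visits, with the residual code reviewed case by case. The FAS list has three items: no study intervention given, fraudulent data, and "missing laboratory (Immunology) assessment (missed visit, blood draw not done at visit, sample not available for testing, result not available"). Invalid consent is not among them. SAP 16.2 runs the secondary immunogenicity analyses on the FAS.

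**The concern.** A deviation summary should show, among other things, how many randomised participants turned out not to qualify. If the population for that table is restricted to people who qualify, it cannot do so.

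The count matters in this trial. Protocol 5.1 and 5.2 treat eligibility deviations as a threat to scientific integrity and regulatory acceptability. Inclusion criterion 4 and exclusion criterion 12 turn on the number and timing of earlier MenACWY doses, yet protocol 8.3.1 lets people enter without written vaccination records. Ineligibility found after randomisation is therefore plausible.

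The consent gap raises a different issue. The SAP treats a participant's data as unusable for safety and for the primary analysis, but its FAS list leaves the same participant in the secondary immunogenicity results.

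**Working it through.** The plan states no figure on this point, and no alpha, power or sample size depends on it. The check is of set membership.

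**Step 1. Three versions of ENR among consented people.**
- Protocol: randomised OR dosed OR invasive procedure.
- SAP, reading A (natural): eligible AND (randomised OR dosed OR invasive procedure).
- SAP, reading B (AND binds before OR): (eligible AND randomised) OR dosed OR invasive procedure.

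A blood draw is taken to be an invasive procedure; this is an assumption. The Schedule of Activities places the Visit 1 blood draw before vaccination.

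| Participant | Protocol ENR | SAP ENR, A | SAP ENR, B | ES |
|---|---|---|---|---|
| Randomised, ineligible, dosed | in | out | in | in |
| Randomised, ineligible, bled, not dosed | in | out | in | out |
| Randomised, ineligible, neither bled nor dosed | in | out | out | out |
| Randomised, eligible | in | in | in | in if dosed |
| Screen failure, no invasive procedure | out | out | out | out |
| Screen failure, ineligible, invasive procedure | in | out | in | out |
| Screen failure, eligible but not entered, invasive procedure | in | in | in | out |

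**Step 2. Effect on the tables.** Let k be the number of randomised participants found ineligible; the documents give no value for k. Under the protocol definition, the ENR summary shows k for code 2. Under reading A it shows 0 for any k, and disposition omits the same k people. With the target of 1206 randomised, each unreported violator is 1/1206 = 0.08% of the trial. Under reading A, dosed violators are in the ES but not in ENR, so the ES is no longer nested in ENR. Under reading B, only violators who were neither dosed nor bled are lost.

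**Step 3. Consent.** Take a participant who was dosed, has a post-vaccination titer, has invalid consent and no fraud finding. Applying the Appendix 3 lists in turn:
- ES: out
- Unsolicited and solicited safety sets: out
- FAS: in
- PPS: out

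By the definitions in SAP 5.3 and 5.4, the FAS lies inside the ES, since both require at least one dose. The Appendix 3 lists break that nesting.

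**Step 4. After correction.** Without the eligibility condition, SAP ENR equals protocol ENR in every row of the table. With invalid consent on the FAS list, the participant in Step 3 is out of all the sets listed there.

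**The case against.** The strongest reply is that this is a wording slip with little behind it. Four parts of that reply deserve an answer.

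- **Ambiguity.** Reading B keeps dosed and bled violators in ENR, so a zero count is not certain. This stands. But two readings that give different tables are themselves a reason to correct the sentence.
- **Scope of the zero.** A reader might infer that the whole eligibility category of the deviation table is emptied. It is not. Category 2 in Table 3 also holds codes 7A, 7B and 8A, which can arise in eligible participants. Only code 2 is affected.
- **Screen failures.** A reader might also infer that the SAP's condition is why screen failures cannot appear in the ENR disposition table. The documents do not support that. Protocol 5.4 defines screen failures as not randomised, so the protocol's own ENR admits them only after an invasive procedure, and the protocol glossary by default treats screened non-participants as not enrolled. The SAP condition changes the status only of ineligible screen failures who had such a procedure. Reporting screen failures by group on the enrolled population is the instruction of protocol 9.4.2, which SAP 9.1 repeats.
- **Traceability.** It would be too strong to say that violators, or their PPS exclusions, could not be traced. The deviation listing, the listing for PPS exclusions and the analysis-set exclusion listings all remain. What is lost is the summary count.

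On consent, the other side can say that the sponsor confirms all exclusions before unblinding (Appendix 3), that more detail sits in a deviation management plan not available here, and that the secondary analyses carry no formal hypothesis. Each limits the consequence. None supplies a reason for the FAS to differ from the other sets.

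**Conclusion.** Both inconsistencies are real in the current texts, and both are minor. The SAP's ENR definition departs from the protocol without saying so. On its natural reading, it forces code 2 to zero in the ENR deviation summary and removes randomised ineligible participants from disposition. The FAS exclusion list lacks an item that the SAP applies to the ES, both safety sets and the PPS.

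It would be wrong to infer any effect on the primary conclusion. Protocol 9.4.3.1 and SAP 16.1.3 base both non-inferiority families on the PPS, which excludes eligibility and consent deviations. Alpha, power and sample size are unchanged.

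The size in practice depends on how many randomised participants prove ineligible and how many consents prove invalid. The documents give neither number. The zero for code 2 rests on reading A. The consent finding rests on the Appendix 3 lists being complete as printed.

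**What to change.** 1. In SAP 5.2, delete the eligibility condition so that the definition matches protocol Table 15. This also removes the ambiguity and restores randomised ineligible participants to the ENR summaries.
2. In SAP Appendix 3, add invalid informed consent to the FAS exclusions, in line with the ES, safety-set and PPS rules.

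Both are SAP wording changes to make before unblinding, plus the matching edits to the programs that derive the sets. Neither needs new data or alters the design. They do not settle how screen failures are displayed. Moving those out of the by-group ENR table would depart from protocol 9.4.2 and would have to be declared separately.

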## 5.3. EXPOSED SET [ES]

The exposed set (ES) will contain all participants who received at least 1 dose of the study intervention.

The allocation in a group is done according to all administered interventions. If there is any doubt whether a participant was vaccinated or not, they will be assumed vaccinated for the purposes of analysis. Participants will be classified according to intervention received.

## 5.4. FULL ANALYSIS SET [FAS]

The FAS will contain all participants who received at least 1 dose of the study intervention and have post-vaccination immunogenicity data, i.e., available hSBA titer for at least one serogroup (A, B, C, W or Y).

For analyses and displays based on the FAS, participants will be classified according to the randomized intervention.

---

Document: C:\ProgramData\activePDF\Temp\DocConverter\API\input\99638a57dafd\$76D9DDEF7D8D4E7C  
B4DEE6C228977964.docx

Author: PPD

Version Number: Final 5.0

**CONFIDENTIAL** Version Date: 05SEP2022

Note: The intent-to-treat principle is preserved, despite the exclusion of participants randomized who did not receive the study intervention, because the decision of whether or not to begin the intervention could not be influenced by knowledge of the assigned intervention, i.e. the study medication is blinded.

## 5.5. PER PROTOCOL ANALYSIS SET [PPS]

The PPS will contain all participants who received at least 1 dose of the study intervention to which they are randomized and have post-vaccination data (FAS) minus participants with protocol deviations that lead to exclusion from the PPS, as defined prior to analysis.

## 5.6. SAFETY ANALYSIS SETS

In case of a vaccination error (wrong vaccine), participants will be analyzed as “treated” (i.e., according to the vaccine a participant receives, rather than the vaccine to which the participant is randomized).

### 5.6.1. UNSOLICITED SAFETY ANALYSIS SET [USS]

The unsolicited safety analysis set (USS) will contain all participants who received at least 1 dose of the study intervention (ES) that report unsolicited AEs/report not having unsolicited AEs.

### 5.6.2. SOLICITED SAFETY ANALYSIS SET [SSS]

The solicited safety analysis set (SSS) will contain all participants who received at least 1 dose of the study intervention (ES) who have solicited safety data.

### 5.6.3. OVERALL SAFETY ANALYSIS SET [OSS]

The overall safety analysis set (OSS) will contain all participants who are in the Solicited Safety Set and/or Unsolicited Safety Set.

## 5.7. OVERVIEW OF ANALYSIS BY PROTOCOL DEVIATION (PD)

---

Document: C:\ProgramData\activePDF\Temp\DocConverter\API\input\99638a57dafd\$76D9DDEF7D8D4E7C  
B4DEE6C228977964.docx

Author: PPD

Version Number: Final 5.0

**CONFIDENTIAL** Version Date: 05SEP2022

Details of PDs can be found in the Protocol Deviation Management Plan and in APPENDIX 3 of this SAP.

## 6. GENERAL CONSIDERATIONS

Immunogenicity and safety endpoints will be summarized descriptively (frequency and percent for categorical data; and number of participants with non-missing observations, mean [or geometric mean], standard deviation [SD] [or geometric standard deviation {GSD}], median, minimum, and maximum for continuous data, unless specified otherwise) at all relevant study visits, as appropriate. In summary tables for categorical data for which categories are defined on the electronic case report form (eCRF), all categories will be presented as specified, even if the participant count within that category is zero.

Unless otherwise specified, all data collected during the trial will be presented in the data listings.

### 6.1. REFERENCE START DATE AND STUDY DAY

Study Day will be calculated from the reference start date and will be used to show start/stop day of assessments and events.

Reference start date is defined as the day of the first dose of study medication, (Day 1 is the day of the first vaccination).

- If the date of the event is on or after the reference date then:
  - Study Day = (date of event – reference date) + 1.

In the situation where the event date is partial or missing, Study Day, and any corresponding durations will appear partial or missing in the data listings.

### 6.2. BASELINE

Unless otherwise specified, baseline is defined as the last non-missing measurement taken prior to reference start date (including unscheduled assessments). In the case where the last non-missing measurement and the reference start date coincide, that measurement will be considered pre-baseline, but Adverse Events (AEs)

---

Document: C:\ProgramData\activePDF\Temp\DocConverter\API\Input\99638a57dafd\$76D9DDEF7D8D4E7C  
B4DEE6C228977964.docx

Author: PPD

Version Number:

Final 5.0

**CONFIDENTIAL** Version Date:

05SEP2022

and medications commencing on the reference start date will be considered post-baseline.

### 6.3. RETESTS, UNSCHEDULED VISITS AND EARLY TERMINATION DATA

Not applicable.

### 6.4. WINDOWING CONVENTIONS

The following table describes assignment of visit windows to the following data for purposes of the immunogenicity analysis:

**Table 2 Visit Windows for Immunogenicity by Visit**

Assigned Study Day (Inclusive)		Visit Assigned	Day Assigned	Month Assigned
From	To			
1 (pre-vaccination)	1 (pre-vaccination)	Visit 1	1	Baseline
24	59	Visit 2	31	Month 1
173	208	Visit 3	181	Month 6
24*	59*	Visit 4	Visit 3 + 31	Month 7

\* Based on number of days from visit 3

### 6.5. STATISTICAL TESTS

The default significance level will be (5%); confidence intervals will be 95% and all tests will be two-sided, unless otherwise specified in the description of the analyses.

### 6.6. COMMON CALCULATIONS

**Geometric Mean Titer/Concentration (GMT/GMC)**

Distributions of antibodies are generally skewed to the right (Nauta, 2010). Therefore, prior to any statistical analysis that assumes normally distributed observations, antibody titers or concentrations will be log10-transformed. GMTs [/GMCs] and their 95% CIs are computed by exponentiating (base 10) of the log10 titers.

The GMT [/GMC] will be calculated using the following formula:

$$10^{\left(\frac{\sum_{i=1}^n \log_{10}(t_i)}{n}\right)}$$

Where  $t_1, t_2, \dots, t_n$  are  $n$  observed immunogenicity titers/concentrations.

